Evaluation of Routine Administration of Glycerin Suppositories to Improve Bowel Function in Patients with Uncomplicated Gastroschisis

NCT03355326

Last date of Revision 5/7/2018

Last date of Approval 4/1/2020

NCT03355326

Introduction/Background:

Gastroschisis is a congenital defect of the abdominal wall that leads to evisceration of various amounts of the abdominal organs. The mainstay of therapy is restoring continuity of the abdominal wall, either through primary closure or with a synthetic graft when primary closure is not feasible. Closure of the abdominal cavity is confounded by prenatal loss of abdominal domain coupled by resultant swelling of the abdominal viscera due to prenatal exposure to amniotic fluid. Additionally, some patients with gastroschisis have other concomitant abnormalities of the bowel (termed complicated gastroschisis) that require additional surgical intervention. It is well established that bowel function after repair of gastroschisis is impaired due to the aforementioned pathologic processes. Previous studies have shown that the time from surgery to attaining full nutrition through enteral means is a predictor for morbidity in this population. Numerous therapeutic interventions have been proposed to help hasten bowel function and decrease the time to tolerance of total enteral nutrition. A common, but unproven, technique is the use of glycerin suppositories to stimulate bowel function.

Study Procedures:

The purpose of this study will be to determine whether routine use of glycerin suppositories improves bowel function as measured by time to full enteral feeds (primary outcome: defined as enteral feed volume ≥120mL/kg/day with appropriate weight gain) in neonates with uncomplicated gastroschisis. Additional secondary outcomes that will be measured include time to first bowel movement, length of hospital stay, infectious complications, days on total parenteral nutrition (TPN), post-operative days on TPN, sequela of long term TPN administration, and post-operative complications.

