Assuming the average time to full enteral feeds in the control group will be approximately 21 days with a standard deviation of 3 days and a power $(1-\beta)$ of 0.8, the study will need to enroll thirty-seven (37) in each study arm to detect a difference of two days between groups (two sided test with an $\alpha = 0.05$). After reaching this enrollment, that data from each group will be analyzed for normality and if found to be normal, student's t-tests will be performed to determine significance for the primary outcome variables. If the resulting data is not normally distributed, Wilcoxon ranked-sum tests will be performed. Data analysis will be completed by [name]., M.P.H.

The average number of uncomplicated gastroschisis patients admitted to Riley Hospital for Children is approximately 20 per year. Assuming 80% enrollment (i.e. 44 patients enrolled) with an 85% retention rate to completion (i.e. 37 patients completing the study), the study period will be approximately 5.5 years.

Participant Privacy/Data Safety

All data obtained for use in this study will be abstracted from clinical (medical record) and entered on to a RedCap database built explicitly for this research study. Data entry will occur on the private/encrypted pediatric general surgery research computer, which is available only in the Pediatric General Surgery office within the physical/technical infrastructure of Indiana University Health. Additionally these computers are independently password-protected and all access to the office is

NCT03355326

limited to staff only and is continuously supervised. All office doors are locked during non-business hours. Patient names will never be used in the research database in order to help reduce the risk of loss of confidentiality. All physical charts will be reviewed (if needed) in this office and only in this office and delivered immediately back to their respective sites upon completion of review. Paper records will be locked within the pediatric general surgery research office at all times.

NCT03355326

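### Days to full feeds is undefined for an infant who does not reach them, and the sizing implies a completers-only comparison that can be biased in either direction

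*Combined protocol and SAP*

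**What the plan says.** Study Procedures makes the primary outcome "time to full enteral feeds (primary outcome: defined as enteral feed volume ≥120mL/kg/day with appropriate weight gain". Introduction/Background states that "the time from surgery to attaining full nutrition through enteral means is a predictor for morbidity in this population".

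Power Analysis/Recruitment Period assumes that the "average time to full enteral feeds in the control group will be approximately 21 days" "with a standard deviation of 3 days" and requires 37 infants per arm "to detect a difference of two days between groups". If the data are normal, "student's t-tests will be performed to determine significance for the primary outcome variables"; otherwise a Wilcoxon rank-sum test is used. The recruitment paragraph takes 44 enrolled and an "85% retention rate to completion (i.e. 37 patients completing the study".

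The plan names no analysis set, no end of follow-up, and no value, rank or censoring rule for an infant without an observed time to full feeds. The one explicit removal after randomisation, in Study Procedures, is for significant rectal bleeding during treatment. No reasons for the 15% loss are given, and no split by arm.

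**The concern.** A t-test or rank test needs a number for each infant. An infant who is not seen to reach the milestone has none, so unless a rule says otherwise that infant drops out of the comparison. The enrolment arithmetic points the same way: it inflates to 44 so that 37 remain, and 37 is what the test needs.

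This would matter little if loss were unrelated to feeding. The plan's own background gives reason for doubt: bowel function after repair is impaired, slower attainment goes with morbidity, and a slow infant has more time in which to be lost. If so, the missing infants carry information about the outcome, and the comparison of those who remain is no longer protected by randomisation. The trial could lose power for a real effect, or show a benefit that is not there.

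The gap can arise in both arms and would remain if the rectal-bleeding removal rule were changed.

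**Working it through.** **Inputs from Power Analysis/Recruitment Period:** control mean 21 days, SD 3, difference 2 (so treated mean 19), two-sided alpha 0.05, power 0.80, 44 enrolled, 85% retained. **Assumptions:** normal times, SD 3 in both arms, and the loss patterns below. The documents give no loss pattern.

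**1. The plan's figures reproduce.** n per arm = 2(1.96 + 0.842)² × 3²/2² = 35.3, or 36 by the normal formula. The t-test solution is 36.3, rounded up to 37, with power 0.808. For loss, 37/0.85 = 43.5, so 44; and 44 × 0.85 = 37.4. Accrual is 20 × 5.5 × 0.8 = 88, so the 44 is per arm.

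**2. Common day cut-off.** Suppose infants not at full feeds by day c are lost. The mean of those who remain is μ − σλ, with a = (c − μ)/σ and λ = φ(a)/Φ(a). Choose c to lose 15% of controls: c = 21 + 3 × 1.036 = 24.11.
- Control: a = 1.036, λ = 0.274, mean 21 − 3 × 0.274 = 20.18.
- Treated: a = 1.703, λ = 0.098, mean 19 − 3 × 0.098 = 18.71; loss 4.4%.
- Difference 20.18 − 18.71 = 1.47 days. Overall loss (15 + 4.4)/2 = 9.7%.

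Power, by simulation with 44 per arm:

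| Controls lost | Completer difference (days) | Completer t-test power | Wilcoxon power, all 44 per arm, non-attainers ranked longest |
|---|---|---|---|
| 5% | 1.76 | 0.81 | 0.84 to 0.86 |
| 10% | 1.60 | 0.75 | 0.84 to 0.86 |
| 15% | 1.47 | 0.71 | about 0.85 |
| 20% | 1.36 | 0.65 | 0.84 to 0.86 |

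If the cut-off is instead set so that overall loss is the plan's 15% (day 23.3; 22% of controls, 8% of treated), the difference is 1.31 days and power about 0.63, against about 0.84 with ranking.

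**3. Equal slow fraction lost.** If the slowest 15% of each arm are lost, both means fall by 3 × 0.274 = 0.82 days. The difference stays at 2.00 and the SD falls to 2.40. Loss of 15% unrelated to outcome also leaves 2.00 days, with power of about 0.80 to 0.82.

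**4. Loss in the treated arm only.** Losing the slowest 15% of treated infants gives 19 − 0.82 = 18.18, so a difference of 21 − 18.18 = 2.82 days. With no true effect, the same loss produces a spurious 0.82-day benefit. Simulated with the slowest 7 of 44 treated infants removed, the completer t-test has a type I error of about 0.27 to 0.30. Ranking those infants longest gives about 0.04.

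**5. Check on the remedy.** If 15% per arm are lost for reasons unrelated to outcome and are nonetheless ranked longest, Wilcoxon power falls to about 0.56 to 0.58, against about 0.80 to 0.81 for the completer t-test. Longest rank therefore suits only infants known not to have reached full feeds.

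**The case against.** A reader might infer that the slowest infants drop out and that the treatment effect is therefore understated. The documents do not support that. They give no reasons for the 15%, and they do not list death, transfer or discharge on parenteral nutrition among the reasons for loss. Other routes are visible in the text. Randomisation takes place on or before the day of surgery, and a secondary abnormality needing surgery is an exclusion, so some infants may prove ineligible afterwards. The stated removal for rectal bleeding is tied to suppository treatment, so it falls in practice on the treated arm; if those infants feed slowly, the effect would be overstated.

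Nor do the documents drop anyone at day 24. Suppositories continue until full feeds, which suggests observation driven by the event. Under the plan's own normal distribution only about 1% of controls would still be short of full feeds at day 28 and 0.1% at day 30. With 5% of controls lost at a cut-off, completer power is 0.81, which meets the target. The ranked-test power of about 0.85 uses all 44 per arm and should not be set against the planned 0.80 as though both used the same number.

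The completer set, too, is implied by the sizing and not named; the analysis sentence refers only to the data from each group.

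All of this stands, and it limits what can be said about direction and size. It does not supply the missing rule. A time-to-event analysis with death as a competing event would be a reasonable alternative to worst ranks, but the plan specifies neither.

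**Conclusion.** The gap is certain: the primary outcome is undefined for infants who do not reach full feeds or who leave, no analysis set is named, and the sizing leads to a comparison of completers. Its effect is not certain. Depending on who is lost, a true 2-day difference could appear as 1.47 days (power about 0.71), 2.0 days or 2.82 days. With no true effect, loss confined to the slowest treated infants could raise the type I error to about 0.27 to 0.30. These are illustrations under normal times, SD 3 and 44 per arm with assumed loss patterns. They are not forecasts, and no single direction of bias can be claimed. The sample size of 37 per arm is not in question. The plan should be amended on this point; confidence in the size of the problem is moderate.

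**What to change.** - Define the primary analysis set as all randomised infants, analysed as randomised.
- Follow each infant in the medical record to full feeds, death or a post-closure day that the investigators fix in advance. Continue to record the outcome after removal from the study, as far as consent allows.
- Make the Wilcoxon rank-sum test, already named in the plan, the primary test. Rank as longest the infants known to have died or not to have reached full feeds by that day. Report medians.
- Do not rank infants of truly unknown status (for example consent withdrawn or records unavailable) as longest. Prespecify how they are handled, for instance by censoring at last known status in a log-rank sensitivity analysis, and report their number by arm.
- Keep the completer t-test as a sensitivity analysis.

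The cost is a wording amendment and one status and date field in the REDCap database; the data already come from the medical record, and no extra patients or blood draws are needed. The headline result becomes a rank comparison with medians in place of a mean difference in days, and power falls if many infants have unknown status.
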